## 11.2.4 Efficacy Analyses

The efficacy endpoints will be evaluated using RECIST Version 1.1.

#### 11.2.4.1 Primary Endpoint

The primary endpoint of the study is invPFS.

invPFS will be calculated as 1+ the number of days from the date of randomization to disease progression, as determined by the investigator or death due to any cause, whichever occurs first. Patients without a documented event of progression will be censored on the date of their last adequate tumor assessment (i.e., radiologic assessment) or date of randomization if no tumor assessments have been performed.

Kaplan-Meier methodology will be used to summarize invPFS. The stratified logrank and the HR will be used for comparing the invPFS distributions among the CO-1686 and erlotinib-treated patients. The invPFS analysis will be stratified by EGFR mutation status (L858R, exon 19 deletion, or other) and territory of residence at time of randomization (Asia vs non-Asia). If the exon 19 deletion subgroup or other mutation subgroup has fewer than 30 patients than these subgroups will be combined for this analysis.

A PFS sensitivity analysis based on an independent radiographic review (irrPFS) will be performed. The irrPFS is defined as the time from randomization to disease progression according to RECIST v1.1 as assessed by independent radiographic review, or death due to any cause, whichever occurs first.

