## 11.3 Sample Size Considerations

Up to 1,200 patients will be randomized in a 1:1 ratio to receive treatment with CO-1686 or erlotinib. In the Phase 2 part, 200 patients will be randomized 1:1 to either CO-1686 500 mg BID or erlotinib 150 mg QD. In the Phase 3 part, up to 1,000 additional patients will be randomized 1:1 to either CO-1686 500 mg BID or erlotinib 150 mg QD into the single (sponsor)-blinded part of this clinical study.

The primary objective of this study is to estimate the relative improvement in PFS for CO-1686 as compared with erlotinib. The median PFS for erlotinib in this patient population is expected to be approximately 10 months. If CO-1686 has a 13 month median PFS then the HR comparing CO-1686 with erlotinib will be approximately 0.80.

For the Phase 3 part of the study, a total of 640 PFS events will provide approximately 80% power to detect a HR of 0.80 at a 0.025 (1-sided) significance level for the comparison of CO-1686 versus erlotinib.

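### The invPFS censoring sentence does not exempt deaths, so it conflicts with the event definition for patients who die without documented progression

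*Combined protocol and SAP*

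**What the plan says.** Section 11.2.4.1 (Primary Endpoint) measures invPFS from randomization to disease progression "as determined by the investigator or death due to any cause, whichever occurs first". The censoring rule follows directly: "Patients without a documented event of progression will be censored on the date of their last adequate tumor assessment". Where a patient has had no scan at all, the randomization date is used instead.

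The same section defines the sensitivity endpoint, irrPFS, as progression "as assessed by independent radiographic review, or death due to any cause, whichever occurs first". It gives irrPFS no censoring rule of its own.

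The counts that depend on the event definition are in two places. Section 11.3 states that "a total of 640 PFS events will provide approximately 80% power to detect a HR of 0.80"; the test is one-sided with alpha 0.025. Section 11.4 ends the study once at least 70% of the randomized Phase 3 patients have had a PFS event.

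The Synopsis and Sections 4.2.1, 11.2.1, 11.3 and 11.4 add no other PFS censoring rule.

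**The concern.** The event has two components, progression and death, but the censoring sentence tests for only one. A patient who dies with no documented progression satisfies both rules, and they give different outcomes: an event at death, or a censored time at the last scan.

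Such patients are plausible under this protocol. Scans are 8 ± 1 weeks apart, suspected clinical progression has to be confirmed by CT or MRI (Section 5.1.2), and Appendix A classes decline without objective evidence as symptomatic deterioration rather than progression. A patient can therefore decline and die between scans.

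Censoring such a patient at the last scan is informative, because the patient leaves the risk set on account of the outcome being measured. The estimand also changes from PFS to time to progression. If the ambiguity is settled only after deaths by arm are visible in an open-label trial, the choice could be criticized as data-dependent.

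**Working it through.** **1. The two rules side by side (Section 11.2.4.1)**

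| Patient | Event definition | Censoring sentence, read literally |
|---|---|---|
| Documented progression | Event | Not censored |
| Alive, no documented progression | No event | Censored at last adequate scan |
| Died, no documented progression | Event at death | Censored at last adequate scan |

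Only the third row conflicts.

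**2. Other censoring rules in the plan.** Overall survival (Section 11.2.4.2) censors patients with no recorded date of death, which is its own event. Time to symptom worsening (same section) censors patients without an event. The primary endpoint is the only one whose rule names part of its event.

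**3. The randomization fallback.** It applies only when no tumor assessment has been performed, but Section 9.6.2.1 requires a scan at screening. Read literally, a patient with no scan after baseline would be censored at the screening scan, on or before randomization, and the fallback would hardly ever apply. The sentence needs the word post-baseline as well as the exemption for death.

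**4. The planned power.** Inputs from Section 11.3: HR 0.80, one-sided alpha 0.025, 1:1 allocation, 640 events.

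- Schoenfeld events for 80% power: 4 × (1.960 + 0.842)² / (ln 0.80)² = 631. Freedman's formula gives 636.
- Power with d events = Φ(√(d/4) × ln 1.25 − 1.960). At d = 640 this is Φ(2.823 − 1.960) = 80.6%.

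The plan's figure is reproduced.

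**5. What the literal rule could do to power.** The share of PFS events that are deaths without documented progression is not in the documents, so a range is assumed. The HR is held at 0.80. Events are accrued under the definition, and these deaths are then removed. The 700 column is 70% of 1,000 patients, using the Section 11.4 rule at full enrollment.

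| Assumed share | From 640 events | Power | From 700 events | Power |
|---|---|---|---|---|
| 2% | 627 | 79.8% | 686 | 83.2% |
| 5% | 608 | 78.6% | 665 | about 82% |
| 10% | 576 | 76.4% | 630 | 80.0% |
| 15% | 544 | 74.0% | 595 | 77.7% |
| 20% | 512 | 71.4% | 560 | 75.2% |

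Whether power falls below about 80% depends on the assumed share and on which target stops the trial. If the literal rule also governed the event count, censored deaths would not count and follow-up would run until enough progressions had accrued, so this calculation would not apply. It would not apply either if enrollment stopped early at 600, 700 or 800 patients, where 70% is 420, 490 or 560 events and 640 is no longer the baseline.

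**The case against.** The strongest reply is that the section already supplies the meaning. Death is named as an event in the sentence before, irrPFS repeats it, and the phrase about an event of progression is probably loose wording for a PFS event, the term used in Sections 11.3 and 11.4. A programmer would have to override an explicit definition in order to censor deaths. This stands as evidence of intent, and it settles which sentence to correct. It does not remove the conflict, because the censoring sentence is a stated rule and nothing elsewhere overrides it.

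Three stronger readings are tempting, and the documents do not support them:

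- *The trial loses power.* The share of deaths is assumed. At 700 events, losing 5% to 10% leaves 665 to 630 events and about 82% to 80% power, which is no shortfall from the stated figure.
- *The rule favors CO-1686 because of its QTc and pneumonitis risks.* No imbalance between arms in deaths without progression is documented. In the earlier study (Section 3.2.1), 8 of 11 deaths were due to NSCLC progression, all 11 were assessed as unrelated to study drug, and both pneumonitis cases resolved. The protocol says that the Investigator's Brochure supersedes these data.
- *Early deaths would be censored at day 1.* The mandatory screening scan means that the literal wording points to that scan, not to randomization.

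It is also fair to say that development for NSCLC has been discontinued and no more patients will be enrolled (Appendix D), so Phase 3 power carries little practical weight. Section 11 remains in force, however, and any invPFS analysis of patients already randomized needs one rule.

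**Conclusion.** The conflict is real and limited to patients who die without documented progression. The censoring sentence is wrong as written: programmed literally, it would deliver time to progression with informative censoring at death in place of the PFS that the section defines. A reader might infer that the sponsor intends to censor deaths. The event definition and the irrPFS wording point the other way.

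The size and direction of any effect on the hazard ratio cannot be determined from the documents, and no loss of the stated 80% power is shown. The power range in the working rests on an assumed share of deaths and a constant HR of 0.80. The 640-event calculation itself is sound. What justifies the correction is that a primary endpoint should have one reading, fixed before analysis.

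**What to change.** Replace the censoring sentence in Section 11.2.4.1 with wording such as:

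> A patient with neither documented progression nor death is censored at the last adequate post-baseline tumor assessment, or at randomization if there is none. Death without documented progression is an event on the date of death.

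State that the same rule applies to irrPFS, with progression taken from the independent review. State also that PFS events counted toward the 640-event target (Section 11.3) and the 70% target (Section 11.4) follow this definition.

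The cost is one replaced sentence and two short cross-references. Scan schedules, data collection and the sample size do not change.

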## 11.2.4.2 Secondary Efficacy Endpoints

#### **OBJECTIVE RESPONSE RATE**

The ORR is the proportion of patients with a best overall response of partial response (PR) or CR recorded from the start of the treatment until disease progression or recurrence. The frequency and percentages of patients with a best overall response of CR, PR, stable disease (SD), or progressive disease (PD) will also be summarized.

The frequency of patients with CR or PR will be compared between treatment groups using the Fisher's Exact Test.

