#### **Efficacy Analysis**

Kaplan-Meier methodology will be used to summarize time-to-event variables. The stratified logrank and HR will be used for comparing the PFS distributions among the CO-1686 and erlotinib treated patients.

The ORR will be summarized with frequencies and percentages.

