# 7.2 Method of Assigning Patients to Treatment Groups

Following confirmation of patient eligibility by the sponsor, patients will be centrally randomized in the ratio 1:1 to receive oral CO-1686 or erlotinib. Patients will be stratified according to presence of sensitizing EGFR mutation (L858R, del19, or other) and territory of residence at time of randomization (Asia vs non-Asia).

The treatment assignment will be generated using the following procedure to ensure that treatment assignment is unbiased. A patient randomization list will be produced by the Interactive Voice/Web Response System (IVRS/IWRS) provider using a validated system that automates the random assignment of treatment. The investigator or his/her delegate will call or log on to the IVRS/IWRS and confirm that the patient fulfills all the inclusion/exclusion criteria. Each package of study drug will contain the unique identification code containing the LOT number and a space for the site to enter the "Subject ID".

Treatment should be initiated on C1D1, which must occur within 3 days (72 hours) of randomization.

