## 9.6.2 Efficacy Evaluations

#### 9.6.2.1 Tumor Assessments

Tumor assessments will be performed at screening, and every  $8 \pm 1$  weeks thereafter (Day 1 of Cycles 3, 5, 7, etc.) until tumor progression, during the baseline period for patients who crossover (Phase 2 part only) to CO-1686 treatment following progression on erlotinib (scans obtained at progression may be used), and at the End-of-Treatment Visit. For patients with clinical progression, radiographic assessment should be performed to document evidence of radiographic progression. Tumor scans do not need to be repeated at end-of-treatment if < 2 weeks since last scan or the patient had disease progression at the last scan. An MRI may be used in place of a CT at end-of-treatment scan if required per local authorities. Scans will be evaluated locally for patient treatment decisions. Scans will also be collected and stored with a

central vendor and quality control performed; central reading of scans will not be done unless requested by the sponsor. Tumor response will be interpreted using RECIST Version 1.1 (Appendix A).

Patients who continue treatment with CO-1686 or erlotinib post-progression should continue to be scanned according to the protocol until they discontinue from the study.

Patients who discontinue treatment without progression should continue to be scanned every  $8 \pm 1$  weeks per protocol until disease progression occurs.

Tumor assessments should consist of clinical examination and appropriate imaging techniques (preferably CT scans of the chest and abdomen with appropriate slice thickness per RECIST Version 1.1); scans of the pelvis (CT or MRI) are required if there is prior evidence of local disease or if clinically indicated (symptomatic patients); other studies (MRI and X-ray) may be performed if required. The same methods used to detect lesions at baseline are to be used to follow the same lesions throughout the clinical study.

Brain imaging (CT/MRI) is required at baseline. Patients with brain lesions detected at baseline will not be eligible for the study. Brain imaging is not required on study unless clinically indicated.

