#### 11.2 Statistical Methods

#### 11.2.1 General Considerations

Quantitative variables will be summarized using descriptive statistics (N, mean, standard deviation, median, minimum, and maximum) and/or frequency and percentages for medically relevant categories. Categorical variables will be presented using frequencies and percentages.

Kaplan-Meier methodology will be used to summarize time-to-event variables. The number of patients with events and the number of censored patients will also be presented. The stratified logrank test will be used to compare the time-to-event distributions between the randomized treatment groups. The same variables used to stratify the randomization will be used in the stratified analyses. In addition, the Cox proportional hazards model will be used to estimate the HR between the randomized treatment groups.

The Fisher's Exact Test will be used to compare frequencies between treatment groups and the t-test will be used for comparing means between treatment groups.

All data will be used to their maximum possible extent but without any imputations for missing data. Results from Phase 2 and Phase 3 will be presented separately and pooled.

All statistical analyses will be conducted with the statistical analysis software (SAS®) system, Version 9.1 or higher.

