#### 11.2.6 Exploratory Analyses

#### 11.2.6.1 Disease Control Rate

The DCR is the percentage of patients with a CR, PR, or SD lasting at least 12 weeks. The frequency and percentages of patients with a best overall response of CR, PR, SD lasting at least 12 weeks, SD lasting less than 12 weeks, or PD will be summarized.

The frequency of patients with CR, PR, SD for > 12 weeks will be compared between treatment groups using the Fisher's Exact Test.

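### ORR and DCR are compared with an unstratified Fisher's exact test, with no between-arm ORR estimate named, although randomization and the primary PFS test are stratified: a small, avoidable loss of efficiency

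*Combined protocol and SAP*

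**What the plan says.** Section 7.2 stratifies the allocation by type of sensitizing mutation (three levels) and by home territory (Asia or elsewhere), giving six strata.

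Section 11.2.4.1 carries both factors into the primary test and adds a pooling rule: "If the exon 19 deletion subgroup or other mutation subgroup has fewer than 30 patients than these subgroups will be combined".

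The plan changes approach with binary endpoints. Section 11.2.1 says that Fisher's exact test "will be used to compare frequencies between treatment groups". Section 11.2.4.2 applies this to ORR, a secondary endpoint: "The frequency of patients with CR or PR will be compared between treatment groups using the" Fisher's test. Section 11.2.6.1 applies it to DCR, an exploratory endpoint: "The frequency of patients with CR, PR, SD for > 12 weeks will be compared between treatment groups", again by Fisher's test. The synopsis says only "The ORR will be summarized with frequencies and percentages". None of these places names a difference, ratio or confidence interval between arms for ORR.

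On how a response is established, section 9.6.2.1 says "Tumor response will be interpreted using RECIST Version 1.1 (Appendix A"). Appendix A makes best overall response depend on confirmation and calls for a further scan 4 ± 1 week after a first CR or PR.

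**The concern.** Mutation type and territory are recorded for every patient at randomization, and the plan treats them as important enough to stratify the allocation and the primary test. Leaving them out of the ORR and DCR comparisons discards information at hand, and a bare Fisher p-value does not say how large the ORR difference is or how precisely it is estimated. What is at stake is some power on one secondary and one exploratory endpoint, and a less informative report.

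A smaller matter sits beside this. If ORR is a confirmed rate, as Appendix A implies, section 11.2.4.2 should say so, and the scan that confirms a response should be identifiable.

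**Working it through.** **The plan's own figure.** The only sample-size statement is for Phase 3 PFS (section 11.3): 640 events, about 80% power, HR 0.80, one-sided 0.025. Schoenfeld's formula gives 4 × (1.960 + 0.842)² / (ln 0.80)² = 631 events; Freedman's gives 636; power at 640 is 80.6%. The figure reproduces and nothing below alters it. No power or alpha is stated for ORR or DCR.

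**Inputs.** From the documents: 1:1 allocation; 100 per arm in Phase 2 and at most 500 per arm in Phase 3; a 58% erlotinib response rate cited as background in the introduction. Assumed, because the documents give no stratum shares or stratum rates: del19/L858R/other 50/40/10%, Asia 40%, the same absolute gain in every stratum, two-sided 5%. Assumed control ORR by mutation: strong gradient 70/55/25% (mean 59.5%), mild 65/57/45% (59.8%), none 60%.

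**Power (%), by simulation.** 'Strata part' is CMH minus the unstratified chi-square; the rest of the gain over Fisher is removal of Fisher's conservatism.

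| Per arm, gain | Gradient | Fisher | Chi-square | CMH, 6 strata | Total gain | Strata part |
|---|---|---|---|---|---|---|
| 100, +15 | strong | 56.5 | 63.0 | 66.1 | 9.6 | 3.1 |
| 100, +15 | mild | 56.2 | 62.5 | 62.9 | 6.7 | 0.4 |
| 100, +15 | none | 56.1 | 62.4 | 61.9 | 5.8 | about 0 |
| 500, +8 | strong | 73.6 | 75.7 | 78.0 | 4.4 | 2.3 |
| 500, +8 | mild | 73.4 | 75.6 | 76.0 | 2.6 | 0.4 |
| 500, +8 | none | 73.1 | 75.2 | 75.1 | 2.0 | about 0 |

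Over gains of 10 to 20 points at 100 per arm, CMH adds 3.4 to 9.6 points over Fisher; over gains of 6 to 10 points at 500 per arm, it adds 1.1 to 5.9. Fisher's actual type I error is 3.1-3.6% at 100 per arm and 3.4-4.2% at 500; CMH's is 4.8-5.2%.

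**Hand check (100 per arm, +15, strong).**
- True SD of the difference, strata fixed: control 0.5×0.70×0.30 + 0.4×0.55×0.45 + 0.1×0.25×0.75 = 0.2228; treated 0.5×0.85×0.15 + 0.4×0.70×0.30 + 0.1×0.40×0.60 = 0.1718; √(0.3945/100) = 0.0628.
- Unstratified null SE: √(2×0.67×0.33/100) = 0.0665. Power Φ[(0.15 − 1.96×0.0665)/0.0628] = 62.3%.
- Stratified null SE: √(2×0.2029/100) = 0.0637, where 0.2029 = 0.5×0.775×0.225 + 0.4×0.625×0.375 + 0.1×0.325×0.675. Power Φ[(0.15 − 1.96×0.0637)/0.0628] = 65.6%.
- Strata part: 65.6 − 62.3 = 3.3 points, against 3.1 simulated.

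**A second set of assumptions**, with rates varying by territory too and a common odds ratio, gives Fisher versus CMH at 100 per arm of 76.3 v 79.6% (no stratum effect), 74.4 v 79.0% (moderate) and 68.8 v 76.2% (strong). At 500 per arm it gives 78.8 v 80.2%, 77.6 v 80.0% and 73.3 v 78.4%.

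**Sensitivity to the share of 'other'.** At 50/30/20% shares and the strong gradient (100 per arm, +15), Fisher/chi-square/CMH is 54.1/60.6/66.1%, so the strata part rises to 5.5 points. This is the most favourable case examined.

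**Effect of the pooling rule.** Under the strong gradient, merging del19 with 'other' gives (0.5×70 + 0.1×25)/0.6 = 62.5%, against 55% for L858R, so little contrast is left. Collapsed CMH power is 62.9%, against 63.0% for the plain chi-square. The chance of fewer than 30 'other' patients among 200 is binomial: 98% if the share is 10%, 47% at 15%, 3% at 20%. Among 1,000 it is 47% at a 3% share and under 0.1% at 5%.

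**Confirmatory scan.** Routine scans at 8 ± 1 weeks are at least 6 weeks apart (one a week late, the next a week early). The confirmation window is 3 to 5 weeks, so an on-schedule scan cannot fall inside it. Take 58% with a first response and a constant hazard, so the share still progression-free is exp(−ln2 / median × weeks × 7/30.44). Confirmed ORR is then 54.4% at 4 weeks and 51.1% at 8 weeks for a 10-month median, or 55.2% and 52.6% for 13 months. The between-arm difference moves from 55.2 − 54.4 = 0.8 to 52.6 − 51.1 = 1.5 points, a shift of 0.7.

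**The case against.** The strongest defence is that nothing here is inconsistent. Section 11.2.1 assigns methods by data type: stratified logrank for times, Fisher's test for frequencies. ORR and DCR follow that rule, and no stated design property is missed. A reader might infer that an unstratified test after stratified randomization is invalid or biased. The documents and the calculation do not support that: the test was specified in advance and its error rate stays below nominal. This part of the defence stands.

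A reader might also infer that ignoring the strata causes the power loss. The table shows otherwise: with a mild gradient the strata contribute 0.4 points, and with none, nothing. Only steep assumed gradients give a visible effect. This stands too.

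It can further be said that a CMH test copying the primary analysis's pooling rule would recover nothing, and that the six-stratum version has cells of 4 and 6 patients per arm and moves to a more powerful test after open-label data exist. These are fair costs. They call for an explicit, dated justification, but they do not argue against reporting a stratified estimate with its interval.

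On confirmation, a reader might see Appendix A as contradicting the schedules. Appendix A states the 8-weekly scans and the confirmatory scan side by side, so it reads as a conditional extra scan left out of Table 9-1, section 9.2.6 and section 9.6.2.1. Appendix D now replaces the Section 9 schedules and allows scans by institutional standard of care. Editing schedules cannot create past scans.

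**Conclusion.** The point holds as a minor matter of efficiency and reporting. Moving from Fisher's test to a six-stratum CMH test is worth about 3-10 power points at 100 per arm and 1-6 at 500 per arm. Most of this reflects Fisher's conservatism. The strata account for about 0-3 points when 'other' is 10% of patients, 5.5 in the steepest case with 'other' at 20%, and none once 'other' is pooled with del19. All these sizes rest on assumed stratum shares and response rates. The missing between-arm ORR estimate and interval does not depend on those assumptions.

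The ORR result is not invalid, and PFS is unaffected. Practical value is limited, since Appendix D says no more patients will be enrolled and the documents do not give the number enrolled.

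The confirmatory-scan gap is editorial. It could move the ORR level by about 3 points and the difference between arms by under 1 point. The constant-hazard assumption probably overstates early progression among responders, but the calculation also leaves out responses that fall back to stable disease.

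**What to change.** In sections 11.2.4.2 and 11.2.6.1:
- Compare ORR and DCR with a CMH test stratified by the randomization factors, and report a stratified risk difference with 95% CI.
- State that all six randomization strata are used without the pooling rule of section 11.2.4.1, and why: pooling del19 with 'other' removes the benefit, while a sparse stratum simply carries little weight in CMH.
- Keep Fisher's test as a reported sensitivity analysis and date the change. Phase 2 is open-label and its monitoring committee includes sponsor personnel, so both results must be shown.

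The cost is a few sentences and no new data. CMH is asymptotic, and a stratum with only responders or only non-responders contributes nothing.

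Separately, the confirmation text in Appendix A must be reconciled with Table 9-1 and its footnotes, sections 9.2.6 and 9.6.2.1, and Appendix D. Section 11.2.4.2 should cite Appendix A and state which subsequent scan, among those already obtained, counts as confirmation.
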